14.1.2 OCULAR DISCOMFORT SCALE (ORA CALIBRA SCALE)

Ocular discomfort scores will be subjectively graded

14.1.3 OCULAR DISCOMFORT & 4-SYMPTOM QUESTIONNAIRE (ORA CALIBRA® SCALE)

Subjects will rate the severity of each of the following symptoms

A series of horizontal black bars of varying lengths, likely representing redacted text or data. The bars are arranged vertically and span the width of the page.

14.1.4 OCULAR SURFACE DISEASE INDEX®

The OSDI® is assessed [REDACTED]
[REDACTED]

Item	Length of Assessment (approx. minutes)
1	120
2	10
3	15
4	10
5	10
6	10
7	10
8	10
9	10
10	10
11	10
12	10

A document page featuring a series of horizontal black redaction bars. A prominent large rectangular redaction box is centered in the upper right quadrant. Below it, a smaller rectangular redaction box is located in the lower right quadrant. The rest of the page is white and devoid of any text or markings.

14.1.5 SYMPTOM ASSESSMENT IN DRY EYE

Subjects will be asked to complete the SANDE Questionnaire

14.1.6 CONJUNCTIVAL ALLERGEN CHALLENGE OCULAR ITCHING SCALE (ORA CALIBRA® SCALE)

Subjects will rate the severity of their ocular itching symptom

14.1.7 LISSAMINE GREEN STAINING (ORA CALIBRA® SCALE)

Subjects will undergo lissamine green staining

30/DEC/2019

Confidential & Proprietary

Page 36 of 51

14.1.8 TEAR FILM BREAK-UP TIME

The TFBUT will be recorded

A series of horizontal black bars of varying lengths, likely redacted content, arranged vertically. The bars are positioned at different heights and widths, creating a pattern of horizontal lines across the page.

15. Safety Analyses

All safety analyses will be conducted using the Safety population.

15.1 Adverse Events

An AE is defined as any untoward medical occurrence associated with the use of an IP in humans, whether or not considered IP-related. An AE can be any unfavorable and unintended sign (e.g., an abnormal laboratory finding), symptom, or disease temporally associated with the use of an IP, without any judgment about causality. An AE can arise from any use of the IP (e.g., off-label use, use in combination with another drug or medical device) and from any route of administration, formulation, or dose, including an overdose.

All AEs will be coded using the MedDRA 22.0.

Treatment-emergent adverse events (TEAE) are defined as any event that occurs or worsens on or after the day that randomized study treatment is initiated. Adverse events recorded in the eCRF which began prior to treatment will not be included in the summary tables but will be included in the AE data listings.

An overall summary will be presented that includes the number and percentage of subjects who experienced at least one AEs, ocular AEs, non-ocular AEs, SAEs, AEs by maximal severity, AEs by relationship to study drug, AEs leading to treatment discontinuation, and AEs resulting in death by treatment arm for the Safety population. In addition, overall TEAEs and the number and percentage of subjects who experienced at least one TEAE, ocular TEAEs, non-ocular TEAEs, TE-SAEs, TEAEs by

maximal severity, TEAEs by relationship to study drug, TEAEs leading to treatment discontinuation, and TEAEs resulting in death by treatment arm for the Safety population.

Separate summaries will be provided for the following categories of AEs:

- Ocular AEs by SOC and PT
- Non-ocular AEs by SOC and PT
- Ocular TEAEs by SOC and PT
- Non-ocular TEAEs by SOC and PT
- Ocular TEAEs by SOC, PT, and maximal severity
- Non-ocular TEAEs by SOC, PT, and maximal severity
- Ocular TEAEs by SOC, PT, and strongest relationship to study drug
- Non-ocular TEAEs by SOC, PT, and strongest relationship to study drug
- Ocular TEAEs by SOC, PT, maximal severity, and strongest relationship to study drug
- Non-ocular TEAEs by SOC, PT, maximal severity, and strongest relationship to study drug
- TEAEs That Led to Premature Discontinuation
- SAEs

Adverse Events and TEAEs will be summarized using discrete summary statistics and presented by treatment arm and all subjects for the the Safety population. If a subject reports the same PT multiple times within the same SOC, that PT will only be reported once within that SOC. As with the PT, if a subject reports multiple conditions within the same SOC, that SOC will only be reported once. In the summary, SOC will be listed in ascending alphabetical order; PTs will be listed in order of descending frequency for all subjects within each SOC.

Severity of an AE is defined as a qualitative assessment of the degree of intensity of an AE as determined by the investigator or reported to him/her by the subject. The assessment of severity is made irrespective of relationship to IP or seriousness of the event and should be evaluated according to the following scale:

- Mild: Event is noticeable to the subject, but is easily tolerated and does not interfere with the subject's daily activities.
- Moderate: Event is bothersome, possibly requiring additional therapy, and may interfere with the subject's daily activities.
- Severe: Event is intolerable, necessitates additional therapy or alteration of therapy, and interferes with the subject's daily activities.

Subjects experiencing more than one AE within a given SOC or PT are counted once within that SOC or PT for the maximal severity.

The relationship of each AE to the study drug should be determined by the investigator using these explanations:

- Definitely Related: Relationship exists when the AE follows a reasonable sequence from the time of IP administration, follows a known response pattern of the drug class, is confirmed by improvement on stopping the IP and no other reasonable cause exists.
- Probably Related: Relationship exists when the AE follows a reasonable sequence from the time of IP administration, follows a known response pattern of the drug class, is confirmed by improvement on stopping the IP and the suspect IP is the most likely of all causes.
- Possibly Related: Relationship exists when the AE follows a reasonable sequence from the time of administration, but could also have been produced by the subject's clinical state or by other drugs administered to the subject.
- Unlikely to be related: Relationship between the AE and IP is more than likely to be unrelated to IP administration but the relationship cannot be definitely attributed to another cause.
- Not Related: Concurrent illness, concurrent medication, or other known cause is clearly responsible for the AE, the administration of the IP and the occurrence of the AE are not reasonably related in time, OR exposure to IP has not occurred.

Subjects experiencing more than one AE within a given SOC or PT are counted once within that SOC or PT for the maximum relationship. All AEs, ocular AEs, non-ocular AEs, and SAEs will be presented in subject listings.

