5 OVERALL STUDY DESIGN

The clinical trial is a Phase 2, multicenter, randomized, double-masked, parallel-group, vehicle-controlled design with block enrollment. Subjects will be randomized to one of the following treatment groups at Visit 2 and will be instructed to follow a dosing regimen QID dosing for four weeks followed by BID dosing for weeks 5-12:

- Reproxalap Ophthalmic Solution (0.25% Novel Formulation)
- Vehicle Ophthalmic Solution (vehicle)

[figure not shown]
Approximately 200 subjects will be randomly assigned to one of the two treatment groups (1:1) to receive either Reproxalap Ophthalmic Solution (0.25% Novel Formulation) or vehicle solution as topical ophthalmic drops administered bilaterally QID for four weeks followed by BID dosing for weeks 5-12. Subjects, Sponsor, CRO and site personnel will be masked to treatment assignment.

[figure not shown]
During the screening period, two 90-minute exposures to the CAE® will be conducted to ascertain eligibility to enter the study. Those who qualify will be randomized to receive study drug in a double-masked fashion for 84 days. Subjects will self-administer drops daily as instructed.

At Visits 3 - 9, no CAE® exposure will occur but signs and symptoms will be assessed.

All subjects will dose with randomized treatment QID between Visit 2 and Visit 5 and switch to BID dosing between Visit 5 and Visit 9.

The total number of expected participants, including screen failures, is approximately 500 subjects.

Subjects who terminate early during the treatment period will be asked to complete safety assessments prior to commencement of alternative DED therapy (if possible). Subjects who are terminated early from the study will not be replaced.

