9.1.4 Procedures for Final Study Entry

Subjects must meet all inclusion and none of the exclusion criteria.

9.1.5 Methods for Assignment to Treatment Groups:

Before the initiation of study run-in at Visit 1, each subject who provides written and informed consent will be assigned to a screening number. All screening numbers will be assigned in strict numerical sequence at a site and no numbers will be skipped or omitted. Each subject who meets all the inclusion and none of the exclusion criteria at Visit 1 and Visit 2 will be assigned a randomization number at the end of Visit 2. The Interactive Web Response System (IWRS) will be used to assign all randomization numbers.

Subjects are to be stratified by Visit 2 (Baseline) [REDACTED] and Visit 2 (Baseline) Pre-CAE fluorescein nasal staining score in the study (worst) eye using the following strata:

- [REDACTED]
- [REDACTED]
- [REDACTED]
- [REDACTED]

[REDACTED] will continue until the sample size for the co-primary analysis described in Section 11.3 has been achieved.

Randomization and kit numbers will be assigned automatically to each subject as they are entered into the IWRS.

The site staff will dispense kit(s) required until the next visit. Both the randomization number and the dispensed study drug kit number(s) will be recorded on the subject's source document and electronic case report form (eCRF). The Sponsor, investigators, and study staff will be masked during the randomization process and throughout the study.

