9.3 Examination Procedures

9.3.1 Procedures to be Performed at Each Study Visit with Regard to Study Objective(s)

Procedures listed below should be performed in the given order. See Appendix 2 on methodologies and grading systems.

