9.3.3 Visit 2: Day 1 – [REDACTED] Confirmation and Baseline

- [REDACTED]
- Study Run-in Collection
- Review of Inclusion/Exclusion Criteria
- Medical/medication history update
- AE query
- Multi-symptom Visual Analogue Scale (VAS)
- [REDACTED]

- [REDACTED]
- [REDACTED]
- [REDACTED]
- BCVA Utilizing an ETDRS Chart
- Slit Lamp Biomicroscopy

- At least 15-minute wait between lissamine green staining and Schirmer's test
- [REDACTED]
- [REDACTED]
- [REDACTED] every 5 minutes thereafter;

- Slit Lamp Biomicroscopy
- Review of Inclusion/Exclusion Criteria
- Randomization
- Study Drug Instillation at the Study Site: All subjects having a positive response (as defined above) and meeting all other screening eligibility criteria at the end of Visit 2 will be randomized to one of two treatment groups utilizing the IWRS system. Randomized subjects will self-administer their initial study drug dose bilaterally at the study site under supervision of a trained technician. Subjects will be instructed to dose four times a day (QID) in both eyes until their next visit.
- Study Drug Dispensation: Prior to discharge from the study site on Visit 2 (Day 1), randomized subjects will be educated on self-administration of study drug. Subjects

will receive their assigned study drug kit with sufficient supply to last until Visit 3 and will be instructed NOT to self-administer study drug on the morning of their next scheduled study visit (Visit 3).

- AE Query
- Subjects will be scheduled for Visit 3.

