11.4.9 Safety Variables

Adverse events will be coded using the MedDRA dictionary.

Frequencies and percentages will be provided per treatment group of subjects with treatment-emergent adverse events (TEAEs), serious TEAEs, and TEAEs causing premature discontinuation. An adverse event is treatment-emergent if it occurs or worsens after the first dose of randomized study treatment. Furthermore, frequencies will be given of subjects with TEAEs by system organ class, by system organ class and preferred term, by system organ class, preferred term and maximal severity, by system organ class, preferred term and strongest relationship, and by system organ class, preferred term, maximal severity, and strongest relationship. Separate analyses will be performed for ocular specific and all adverse events (including systemic).

Other safety endpoints including visual acuity, slit lamp biomicroscopy, intraocular pressure (IOP), tear osmolarity and dilated fundoscopy will be summarized by treatment group and visit using descriptive statistics. Changes or shifts from baseline will also be summarized where appropriate. For assessments performed by eye, worst eye (study eye) and fellow eye will be summarized separately.

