NCS	Not Clinically Significant
OD	Oculus Dexter (Right Eye)
OS	Oculus Sinister (Left Eye)
OSDI	Ocular Surface Disease Index

OU	Oculus Uterque (Both Eyes)
PDF	Portable Document Format
PP	Per Protocol
PPOD	Per Protocol Ocular Dryness
PPFSN	Per Protocol Fluorescein Nasal Score
PT	Preferred Term
QID	Quater in Die (Four Times Daily)
RTF	Rich Text Format
SAE	Serious Adverse Event
SANDE	Symptom Assessment in Dry Eye
SAP	Statistical Analysis Plan
SAS	Statistical Analysis Software
SD	Standard Deviation
SDC	Statistics & Data Corporation, Incorporated
SE	Standard Error
SOC	System Organ Class
SOP	Standard Operating Procedure
TEAE	Treatment-Emergent Adverse Event
TFBUT	Tear Film Break-Up Time
TMF	Trial Master File
VA	Visual Acuity
VAS	Visual Analog Scale
WHODrug	World Health Organization Drug Dictionary

1. Introduction

The purpose of this statistical analysis plan (SAP) is to describe the planned analyses and reporting for protocol ADX-102-DED-013, amendment 1 dated 17 December 2019.

This SAP is being written with due consideration of the recommendations outlined in the most recent International Conference on Harmonisation (ICH) E9 Guideline entitled Guidance for Industry: Statistical Principles for Clinical Trials and the most recent ICH E3 Guideline, entitled Guidance for Industry: Structure and Content of Clinical Study Reports.

[figure not shown]
This SAP describes the data that will be analyzed and the subject characteristics, efficacy, and safety assessments that will be evaluated. This SAP provides details of the specific statistical methods that will be used. The statistical analysis methods presented in this document will supersede the statistical analysis methods described in the clinical protocol. If additional analyses are required to supplement the planned analyses described in this SAP, they may be completed and will be identified in the clinical study report.

[figure not shown]
[figure not shown]
2. Study Objectives

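### SAP 15.1 has two rules that disagree for adverse events starting on Day 1 before the first randomized drop, and its TEAE definition differs from the protocol's

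*SAP*

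**What the plan says.** The protocol (11.4.9 Safety Variables) takes the dose as the boundary: "An adverse event is treatment-emergent if it occurs or worsens after the first dose of randomized study treatment".

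The SAP (15.1 Adverse Events) takes the calendar day, counting "any event that occurs or worsens on or after the day that randomized study treatment is initiated". Its next sentence draws a different line: "Adverse events recorded in the eCRF which began prior to treatment will not be included in the summary tables"; such events go to the listings only.

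The SAP text governs. Its introduction states: "The statistical analysis methods presented in this document will supersede the statistical analysis methods described in the clinical protocol".

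For the order of events on Day 1, protocol 9.3.1 says: "Procedures listed below should be performed in the given order". The Visit 2 list (9.3.3) contains "At least 15-minute wait between lissamine green staining and Schirmer's test", then randomization, then the first supervised dose. Section 5 places the challenge before randomization: "two 90-minute exposures to the CAE® will be conducted to ascertain eligibility to enter the study".

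Protocol 10.1 lists the date of onset among the items to document for each adverse event and names no onset time. It also says that worsening of dry eye signs and symptoms is not reported as an adverse event.

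**The concern.** In many trials it makes little difference whether treatment emergence is counted from the first dose or from the day of the first dose. Here the first randomized drop comes at the end of a long visit with a provocation challenge, a dye and a test strip in the eye. A new ocular complaint that starts during those steps has nothing to do with randomized drug, yet it carries the same date as one that starts after the drop.

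The comparison at stake is ocular tolerability against vehicle, which is part of the objective in protocol section 3. Protocol section 2 describes the known signal as brief, mild to moderate stinging, reported by most subjects in several earlier trials. For an effect of that kind the first dose matters, and Day 1 is where the SAP rules are unclear. Two programmers working from SAP 15.1 could produce different TEAE tables from the same data.

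**Working it through.** The documents give no figure for this point, so there is none to reproduce. The check is a comparison of texts, followed by an illustration with assumed rates.

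**1. What precedes the first drop on Day 1.** Lissamine green staining and Schirmer's test are listed at Visit 2 before randomization. Part of that list is redacted, so the position of the CAE exposure is inferred. Section 5 has two exposures in the screening period and none at Visits 3 to 9. Section 9.1.5 stratifies on the "Visit 2 (Baseline) Pre-CAE fluorescein nasal staining score in the study (worst) eye". Only subjects with a positive response at the end of Visit 2 are randomized. One exposure therefore falls at Visit 2, before the dose.

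**2. The rules side by side.**

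| Event | Protocol 11.4.9 | SAP 15.1, definition | SAP 15.1, next sentence |
|---|---|---|---|
| Starts on Day 1 before the first drop, does not worsen | Not a TEAE | TEAE | Out of summary tables |
| Starts before the first drop, worsens after it | TEAE | TEAE | Out of summary tables |
| Starts in the run-in, does not worsen | Not a TEAE | Not a TEAE | Out of summary tables |
| Starts after the first drop | TEAE | TEAE | Stays in |
| Dry-eye exacerbation | Not an AE | Not an AE | Not applicable |

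The first two rows are in conflict. In the first, the two SAP sentences give opposite answers. In the second, the exclusion sentence, read literally, removes events that both definitions count. SAP 15.1 also plans separate tables of ocular AEs and ocular TEAEs; these would largely coincide if every pre-treatment event were removed. That makes the literal reading hard to sustain throughout the section.

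**3. Whether the data could settle it.** With an onset date alone, the first and fourth rows look identical. Visit 2 shows one AE query near its start and one after dispensing. Together they bracket both the procedures and the dose, so they do not separate the two. The eCRF may record a time; the documents do not say.

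**4. Illustrative size.** Let p be the true post-dose rate in an arm and q the share of subjects, equal in both arms and independent of p, with a pre-dose Day 1 event that is counted.

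- Observed rate: p′ = 1 − (1 − p)(1 − q) = p + q(1 − p)
- Observed difference: (p_R − p_V)(1 − q)

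None of the values of p and q below come from the documents.

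| True rates, R vs V | q | Observed rates | Difference (points) | Ratio |
|---|---|---|---|---|
| 20% vs 10% | 0 | 20% vs 10% | 10.0 | 2.00 |
| | 2% | 21.6% vs 11.8% | 9.8 | 1.83 |
| | 5% | 24.0% vs 14.5% | 9.5 | 1.66 |
| | 10% | 28.0% vs 19.0% | 9.0 | 1.47 |
| 20% vs 5% | 0 | 20% vs 5% | 15.0 | 4.00 |
| | 1% | 20.8% vs 5.95% | 14.85 | 3.50 |
| | 5% | 24.0% vs 9.75% | 14.25 | 2.46 |
| | 10% | 28.0% vs 14.5% | 13.5 | 1.93 |

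With equal true rates (5% in each arm) and q = 5%, both arms show 9.75% and the difference stays at 0.

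**The case against.** A reader might infer from the definition sentence alone that everything the Visit 2 challenge provokes will be tabulated as treatment-emergent. The documents do not support that, for several reasons.

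- **The exclusion sentence.** Read literally, it removes an event that began before the first drop. This stands as a reason not to call the outcome settled. It does not cure the problem, because it contradicts the sentence before it and cannot be applied within Day 1 on onset dates alone.
- **Dry-eye exacerbations are not adverse events.** The visible part of the CAE response criterion is corneal staining, a dry-eye sign, so much of what the challenge elicits reaches no AE table under either definition. This stands. What remains is events of another kind, such as irritation from dye or strip.
- **The relationship tables offer some protection.** SAP 15.1 includes in its Not Related category the case where there has been no exposure to the product, so a pre-dose event should fall there. This stands for the relationship tables. The incidence and severity tables that do not split by relationship have no such safeguard.
- **Dye is used after Day 1 too.** SAP 13.2.1 and 13.3.1 analyse fluorescein staining from Week 1 to Week 6 and from Week 2 to Week 12. Events provoked at those visits are TEAEs under either definition, and a change to the Day 1 rule does not touch them.
- **The size is assumed.** The ratio is the more sensitive scale, and the visible AE plan gives counts and percentages by arm with no ratio or test. On the difference scale the shift is small.

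Nor can it be said that the departure from the protocol went undeclared: SAP section 16, on changes from protocol-stated analyses, is redacted.

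**Conclusion.** The point holds as an inconsistency, both between the two documents and within SAP 15.1, in the definition behind the main safety tables. Events that are not dry-eye exacerbations and start on Day 1 before the first drop can be counted as treatment-emergent, and the timing item named in the protocol cannot identify them.

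The expected consequence is modest: equal inflation of both arms' ocular TEAE rates and some dilution of the contrast. For pre-dose rates of 2% to 10%, an assumed 10-point difference shrinks by 0.2 to 1.0 points. The true rate is not in the documents and may be lower than these values.

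The stronger inference that the SAP would create a false difference between arms is not supported. These events arise before any randomized drug, so in expectation they fall equally on both arms. The conclusion rests on the inferred position of the CAE exposure at Visit 2 and on the eCRF not already recording onset time. The correction is worth making because it is cheap and removes a choice that would otherwise be left to programming.

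**What to change.** 1. In SAP 15.1, use the protocol's definition: onset or worsening after the first randomized dose.
2. Reword the sentence on events that began before treatment so that it refers to the first randomized dose, keeps events that worsen after that dose as TEAEs, and says which summary tables it covers. Pre-dose Day 1 events that do not worsen stay in the AE listings.
3. For Day 1 onsets, record a before/after-first-dose flag or an onset time on the AE form.
4. Count a Day 1 event of unknown timing as treatment-emergent. Without item 3 this default would reproduce the calendar-day rule, so the flag or time is the part that makes the difference.

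The cost is two reworded sentences in the SAP and one extra AE field to complete and query, for Day 1 events only.
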